9.4.7 Presence or absence of splenomegaly

Presence or absence of splenomegaly which are considered to be caused by infiltration of lymphocyte is assessed by CT. To be considered positive, the vertical length of spleen must be >13 cm by CT.

9.4.8 Evaluation of infiltration to bone marrow

Infiltration to bone marrow will be evaluated by PET-CT or bone marrow aspiration or biopsy. When bone marrow evaluation is selected, the results will be categorized into the following:

- Positive: Presence of apparent malignant findings including infiltration of abnormal lymphocyte and abnormality in assembly
- Undetermined: Increase of lymphocyte aggregation without infiltration of abnormal lymphocyte or abnormality in assembly
- Negative: Absence or minimal findings of lymphocyte aggregation.

9.4.9 Postdose Evaluation

Imaging studies will be performed by the same method as screening.

9.4.9.1 *Evaluation of target lesion*

Efficacy for target lesion will be assessed by calculating reduction rate (A) and growth rate (B) of the SPD according to the following formula:

$$(A) = \frac{(C) \text{ at screening} - (C) \text{ at evaluation}}{(C) \text{ at screening}} \times 100$$

$$(B) = \frac{(C) \text{ at evaluation} - \text{minimum (C)}^{*1}}{\text{minimum (C)}^{*1}} \times 100$$

^{*1}: minimum (C) value obtained during the study including the screening

(C) = SPD

9.4.9.2 *Criteria for Response Assessment*

Table 7: Summary of Response Criteria

Response and Site	PET-CT-Based Response	CT-Based Response
Complete	Complete metabolic response	Complete radiologic response (all of the following) Target nodes/nodal masses must regress to <1.5 cm in LD _i No extralymphatic sites of disease
Lymph nodes and extralymphatic sites	Score 1, 2, or 3* with or without a residual mass on 5PS [†] It is recognized that in Waldeyer's ring or extranodal sites with high physiologic uptake or with activation within spleen or marrow (eg, with chemotherapy or myeloid colony-stimulating factors), uptake may be greater than normal mediastinum and/or liver. In this circumstance, complete metabolic response may be inferred if uptake at sites of initial involvement is no greater than surrounding normal tissue even if the tissue has high physiologic uptake	
Nonmeasured lesion	Not applicable.	Absent
Organ enlargement	Not applicable	Regress to normal
New lesions	None	None
Bone marrow	No evidence of FDG-avid disease in marrow	Normal by morphology; if indeterminate, IHC negative
Partial	Partial metabolic response	Partial remission (all of the following)
Lymph nodes and extralymphatic sites	Score 4 or 5 [†] with reduced uptake compared with baseline and residual mass(es) of any size At interim, these findings suggest responding disease	≥50% decrease in SPD of up to 6 target measurable nodes and extranodal sites When a lesion is too small to measure on CT, assign 5 mm × 5 mm as the default value

	At end of treatment, these findings indicate residual disease	When no longer visible, 0mm × 0 mm For a node >5 mm × 5 mm, but smaller than normal, use actual measurement for calculation
Nonmeasured lesions	Not applicable	Absent/normal, regressed, but no increase
Organ enlargement	Not applicable	Spleen must have regressed by > 50% in length beyond normal
New lesions	None	None
Bone marrow	Residual uptake higher than uptake in normal marrow but reduced compared with baseline (diffuse uptake compatible with reactive changes from chemotherapy allowed). If there are persistent focal changes in the marrow in the context of a nodal response, consideration should be given to further evaluation with MRI or biopsy or an interval scan.	Not applicable
No response or stable disease	No metabolic response	Stable disease
Target nodes/nodal masses, extranodal lesions	Score 4 or 5 with no significant change in FDG uptake from baseline at interim or end of treatment	<50% decrease from baseline in SPD of up to 6 dominant, measurable nodes and extranodal sites; no criteria for progressive disease are met
Nonmeasured lesions	Not applicable	No increase consistent with progression
Organ enlargement	Not applicable	No increase consistent with progression
New lesions	None	None
Bone marrow	No change from baseline	Not applicable
Progressive disease Individual target nodes/nodal masses	Progressive metabolic disease Score 4 or 5 with an increase in intensity of uptake from baseline and/or	Progressive disease requires at least 1 of the following PPD progression:
Extranodal lesions	New FDG-avid foci consistent with lymphoma at interim or end-of-treatment assessment	An individual node/lesion must be abnormal with: LDi >1.5 cm and Increase by ;50% from PPD nadir and An increase in LDi or SDi from nadir 0.5 cm for lesions < 2 cm 1.0 cm for lesions > 2 cm

		In the setting of splenomegaly, the splenic length must increase by >50% of the extent of its prior increase beyond baseline (eg, a 15-cm spleen must increase to >16 cm). If no prior splenomegaly, must increase by at least 2 cm from baseline New or recurrent splenomegaly
Nonmeasured lesions	None	New or clear progression of preexisting nonmeasured lesions
New lesions	New FDG-avid foci consistent with lymphoma rather than another etiology (eg, infection, inflammation). If uncertain regarding etiology of new lesions, biopsy or interval scan may be considered	Regrowth of previously resolved lesions A new node >1.5 cm in any axis A new extranodal site >1.0 cm in any axis; if <1.0 cm in any axis, its presence must be unequivocal and must be attributable to lymphoma Assessable disease of any size unequivocally attributable to lymphoma
Bone marrow	New or recurrent FDG-avid foci	New or recurrent involvement

Abbreviations: 5PS, 5-point scale; CT, computed tomography; FDG, fluorodeoxyglucose; IHC, immunohistochemistry; LD_i, longest transverse diameter of a lesion; MRI, magnetic resonance imaging; PET, positron emission tomography; PPD, cross product of the LD_i and perpendicular diameter; SD_i, shortest axis perpendicular to the LD_i; SPD, sum of the product of the perpendicular diameters for multiple lesions.

*A score of 3 in many patients indicates a good prognosis with standard treatment, especially if at the time of an interim scan. However, in trials involving PET where de-escalation is investigated, it may be preferable to consider a score of 3 as inadequate response (to avoid undertreatment). Measured dominant lesions: Up to 6 of the largest dominant nodes, nodal masses, and extranodal lesions selected to be clearly measurable in two diameters. Nodes should preferably be from disparate regions of the body and should include, where applicable, mediastinal and retroperitoneal areas. Nonnodal lesions include those in solid organs (eg, liver, spleen, kidneys, lungs), GI involvement, cutaneous lesions, or those noted on palpation. Nonmeasured lesions: Any disease not selected as measured, dominant disease and truly assessable disease should be considered not measured. These sites include any nodes, nodal masses, and extranodal sites not selected as dominant or measurable or that do not meet the requirements for measurability but are still considered abnormal, as well as truly assessable disease, which is any site of suspected disease that would be difficult to follow quantitatively with measurement, including pleural effusions, ascites, bone lesions, leptomeningeal disease, abdominal masses, and other lesions that cannot be confirmed and followed by imaging. In Waldeyer's ring or in extranodal sites (eg, GI tract, liver, bone marrow), FDG uptake may be greater than in the mediastinum with complete metabolic response, but should be no higher than surrounding normal physiologic uptake (eg, with marrow activation as a result of chemotherapy or myeloid growth factors).

†PET 5PS: 1, no uptake above background; 2, uptake \leq mediastinum; 3, uptake $>$ mediastinum but \leq liver; 4, uptake moderately $>$ liver; 5, uptake markedly higher than liver and/or new lesions; X, new areas of uptake unlikely to be related to lymphoma.

Source: Cheson BD, Fisher RI, Barrington SF, et al. (2014) Recommendations for Initial Evaluation, Staging, and Response Assessment of Hodgkin and Non-Hodgkin Lymphoma: The Lugano Classification. *J Clin Oncol* 32(27):3059–3067

9.4.9.3 *Evaluation of skin lesion by mSWAT*

Criteria for assessment for tumor shrinkage effect on skin lesion by mSWAT are as following:

- CR: 100% clearance of skin lesion*
- PR: 50 to 99% clearance of skin disease from baseline without new lesion
- SD: $< 25\%$ increase to $< 50\%$ clearance in skin disease from baseline without appearance of new lesion.
- PD: $\geq 25\%$ increase in skin disease from baseline or New tumor mass^{**} or Loss of response: in those with complete or partial response, increase of skin score of greater than the sum of nadir plus 50% baseline score.

* In case distinguish between residual lesion and normal skin tissue is difficult, CR is determined after confirming disappearance of skin lesion by biopsy.

** tumor mass : at least 1 cm diameter solid or nodular lesion with evidence of depth and/or vertical growth

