9.4.2 Imaging

Before the start of study drug administration, evaluation by CT images of neck, chest, abdomen, and pelvis that are taken by a pitch of 5 mm preferable (as for neck image, a pitch of 2.5 to 5 mm will be preferred) will be performed. Same imaging techniques should be used at baseline and on study assessment. PET-CT is encouraged, but not required.

9.4.2.1 ***Definition of lesion which can be used for efficacy assessment (evaluable lesion)***

Nodal lesion with the size > 1.5 cm by longest transverse dimension (LDi) on sectional image (e.g. enlarged lymph node) at screening and extranodal lesion which can be followed by imaging are defined as evaluable lesion.

9.4.2.2 ***Definition of lesion which cannot be used for efficacy assessment (non-evaluable lesion)***

Non-evaluable lesion is defined as nodal lesion with $LDi \leq 1.5$ cm on sectional image of CT at screening and extranodal lesion that cannot be followed by imaging.

9.4.2.3 ***Definition of Measurable Lesion (common with nodal and extranodal lesion)***

In evaluable lesions, measurable lesion is defined as the lesion that meets both following criteria:

- The LDi > 1.5 cm on sectional image of CT for nodal lesion; and > 1.0 cm for extranodal lesion
- Definitely measurable by 2 perpendicular dimensions (LDi and its perpendicular dimension) on sectional image of CT

9.4.2.4 ***Definition of Non-measurable lesion***

In evaluable lesions, non-measurable lesion is defined as the lesion that meets any of the following criteria:

- Enlarged lymph node: Lesion with the LDi > 1.5 cm on sectional image of CT, but not definitely measurable by 2 dimensions (LDi and its perpendicular dimension)
- Extranodal lesion: All lesions that can be followed by imaging, but do not meet the definition of measurable lesion

9.4.2.5 ***Nodes or Extranodal Lesions That Split When Disease Is Responding***

If a confluent nodal mass splits into several discrete nodes, the individual product of the perpendicular diameters (PPDs) of the nodes should be summed together to represent the PPD of the split lesion; this PPD is added to the sum of the PPDs of the remaining lesions to measure response. If subsequent growth of any or all of these discrete nodes occurs, the nadir of each individual node is used to determine progression (as if each individual node was selected as a target lesion at baseline).

9.4.2.6 ***Nodes or Extranodal Lesions That Become Confluent When Disease Is Progressing***

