9.4.4 Definition and Selection of Non-target Lesion

Measurable lesions that are not selected as target lesion and non-measurable lesions are defined as non-target lesions.

Non-target lesions are separately evaluated as nodal non-target lesions and extranodal nontarget lesions. If any tumor lesions are found through gastrointestinal endoscopy, the lesion is to be evaluated as extranodal non-target lesion.

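### Table 7's CT complete-response row fails a target node of exactly 1.5 cm, a size the protocol elsewhere does not count as disease, and two neighbouring rules in the table leave cases undecided (minor)

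*Combined protocol and SAP*

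**What the plan says.** **Where a node starts to count as disease.** Section 9.4.2.1 defines an evaluable node as "Nodal lesion with the size > 1.5 cm by longest transverse dimension (LDi) on sectional image"; Section 9.4.2.2 puts a node of 1.5 cm or less in the non-evaluable class. Section 9.4.2.3 sets the measurable threshold the same way: "The LDi > 1.5 cm on sectional image of CT for nodal lesion". Table 7's CT progression column agrees: "An individual node/lesion must be abnormal with: LDi >1.5 cm and". Its entry for a new node also uses >1.5 cm.

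**CR, target nodes (CT column).** "Target nodes/nodal masses must regress to <1.5 cm in" LDi, a strict inequality. This column asks for no percentage fall in the sum of products of diameters (SPD). PR needs a fall of at least 50%; a smaller fall without progression is stable disease.

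**Nonmeasured lesions.** The CR entry is "Nonmeasured lesion Not applicable. Absent", where the last word is the CT rule. The PR entry is "Absent/normal, regressed, but no increase". Section 9.4.4 says "Non-target lesions are separately evaluated as nodal non-target lesions and extranodal nontarget lesions", but Table 7 has a single line for both kinds. The table's footnote describes nonmeasured sites as ones that continue to be regarded as abnormal.

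**Progression increments.** Table 7 gives "0.5 cm for lesions < 2 cm", then 1.0 cm for lesions >2 cm.

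**Use.** The primary endpoint is ORR, CR plus PR (Section 2.3), with the primary analysis on independently reviewed results (Section 5.9). PET-CT is encouraged but optional (Sections 3.1.1 and 9.4.2), so the CT column may be the only one that applies.

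**The concern.** One boundary is written two ways. Four rules place a node of exactly 1.5 cm on the normal side; the CR row alone places it on the other.

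This touches the primary endpoint because CT-based CR and PR rest on different quantities. CR asks whether target nodes have reached normal size; PR asks whether the SPD has halved. A node that starts only slightly enlarged can return to normal size without halving its product, so PR is no fallback and the CR row alone separates responder from stable disease.

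The other two gaps raise the same kind of question. A non-target node that has shrunk to normal size but is still visible may or may not be *Absent*. A lesion of exactly 2.0 cm has no stated progression increment, so the progression date used for PFS and duration of response could depend on the reader. Under Sections 3.1.1 and 3.5.2 a disagreement between site and central reader is settled by choosing one of the two assessments, so an unclear rule can produce avoidable adjudications.

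**Working it through.** **1. The plan's own figure.** Section 5.2 states 89% power to show ORR >10% with 40 patients, a true ORR of 30% and 5% two-sided alpha. An exact binomial calculation reproduces it. The smallest count with an upper tail of 0.025 or less under 10% is 9 of 40 (tail 0.0155; for 8 of 40 it is 0.0419). P(X ≥ 9 | n = 40, p = 0.30) = 0.889. That figure is correct and does not depend on this point.

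**2. When a 1.5 cm node removes a responder.** The SPD reduction is defined in Section 9.4.9.1. For a node shrinking in proportion from LDi = L to 1.5 cm, the fall is 1 − (1.5/L)².

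| Baseline LDi (cm) | SPD fall | As written | With ≤1.5 cm |
|---|---|---|---|
| 1.6 | 12.1% | SD | CR |
| 1.8 | 30.6% | SD | CR |
| 2.0 | 43.8% | SD | CR |
| 2.1 | 49.0% | SD | CR |
| 2.2 | 53.5% | PR | CR |
| 2.5 | 64.0% | PR | CR |
| 3.0 | 75.0% | PR | CR |

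The fall reaches 50% at L = 1.5 × √2 = 2.12 cm. The table assumes that every other CR condition is met.

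With both diameters stated:
- 1.8 × 1.4 to 1.5 × 1.2 cm: 1 − 1.80/2.52 = 28.6%. SD as written; the nodal CR condition is met at ≤1.5 cm.
- 3.0 × 2.0 to 1.5 × 1.2 cm: 1 − 1.80/6.00 = 70%. PR as written, still in ORR.

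**3. Non-target nodes.** Take target nodes that each go from 2.0 × 1.6 to 1.4 × 1.2 cm: 1 − 1.68/3.20 = 47.5%. They meet the target-node CR rule. A non-target node goes from 1.7 to 1.1 cm and is still visible. If *Absent* means not visible, the patient is SD. If a node of normal size is no longer disease, the patient is CR. Under Section 9.4.4 such a node is either a measurable node left over after six targets or an enlarged node that cannot be measured in two dimensions.

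**4. Progression at 2.0 cm.** Nadir 2.0 × 1.5 cm, later 2.6 × 1.8 cm. Product: 4.68/3.00 − 1 = +56%. LDi: +0.6 cm; short axis: +0.3 cm. This is progression under a 0.5 cm increment and not under 1.0 cm. The table assigns neither.

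**5. Size on the ORR scale.** One patient of 40 is 2.5 points. The exact 95% lower limit is 10.8% for 9/40 and 9.1% for 8/40, so one reclassified patient changes the comparison with 10% only at that boundary. The documents give no count of affected patients, so the loss is an assumption shown as a range:

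| Points lost from a true 30% ORR | Exact power, n = 40 |
|---|---|
| 0 | 88.9% |
| 1 | 86.1% |
| 2.5 | 81.0% |
| 5 | 70.0% |

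**The case against.** **Several conditions must coincide.** Loss from ORR through the target-node rule needs CT-only assessment, an LDi of exactly 1.5 cm at best response, target disease small enough that the SPD has not halved, and every other CR condition met. Targets are chosen largest first (Section 9.4.3), so one sizeable node will usually carry the patient to PR. This stands, and it is why the point is minor.

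**Non-target nodes.** A reader might infer that any non-target node still visible counts as residual disease. The documents do not support that as the plain meaning: the Table 7 footnote ties nonmeasured lesions to sites still regarded as abnormal, so a node back to normal size can be read as absent disease. The opposite reading is not excluded either, because the PR entry lists normal beside absent, which would be redundant if absent already covered it. What remains is ambiguity.

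**Symbols.** Two of the three gaps rest on a single < sign, and one comparison sign in the same table came through as a semicolon. Other ≤ and ≥ signs survived, so this does not show that the < signs are wrong, but the original page must be checked. The nonmeasured-lesion ambiguity rests on words and is unaffected.

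**Summary status.** Table 7 is titled a summary, and Sections 3.5.2 and 3.5.4 send reviewers to the cited Cheson criteria, which are not available here. Readers may not have followed the literal boundary. That limits the likely effect, but the protocol should still agree with itself.

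**Conclusion.** The inconsistency at 1.5 cm is real, and it lies in a rule that feeds the primary endpoint. Its usual effect is to turn CR into PR, which leaves ORR unchanged; CR rate on its own is not a listed endpoint. Only in CT-only patients with uniformly small target nodes does it turn a responder into stable disease. The 2.12 cm limit assumes proportional shrinkage of a single node, or of target nodes that all reach 1.5 cm; unequal shrinkage moves it somewhat. The ambiguity over *Absent* and the missing rule at 2.0 cm are separate, smaller gaps.

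A reader might infer that many patients are misclassified or that the stated power is undermined. The documents support neither. They give no count of affected patients, the conditions for loss from ORR are narrow, and the power range above is purely illustrative, with the low end the more plausible. Any loss from ORR is an under-count, against the drug. Severity: minor.

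**What to change.** First check the < signs at 1.5 cm and 2 cm on the original page. If they stand:

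- In the CT CR row, set the target-node rule to ≤1.5 cm in LDi, matching Section 9.4.2 and the progression row.
- State whether a non-target node with LDi ≤1.5 cm satisfies *Absent*, and give nodal and extranodal non-target lesions separate entries, as Section 9.4.4 implies.
- Reconcile the progression increments with the cited response criteria so that every size, including 2.0 cm, falls in exactly one category. These documents do not show which increment applies there, and progression also governs stopping treatment, so no value is proposed here.

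Timing matters. The synopsis planned the last patient in for 3Q 2018, Section 5.1 requires the independent reviews to be finished before the main analysis, and this version is dated July 2021, so the read may already be done. If it is not, settle the wording beforehand; Section 5.1 calls for an amendment if the change is a major one to the primary endpoint definition. If it is done, keep the classification as read and report the boundary cases, reclassified from recorded measurements, as a sensitivity analysis. Loosening CR in the primary analysis after an open-label pivotal study has been read would invite the criticism that the change favours the drug.

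The cost is a few edits to one table and a short listing of boundary cases. No new scans are needed.

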3.0 STUDY ASSESSMENTS

3.1 Efficacy

3.1.1 Primary Efficacy Endpoint

The primary efficacy endpoint is to establish the ORR, defined as the proportion of patients with tumor size reduction of a predefined amount and for a minimum time period, evaluated by using the revised criteria for response assessment in lymphoma [[Cheson 2014](#)] (see Section 9.4).

Tumor assessments will be performed by imaging modalities. CT, magnetic resonance imaging, or PET scanning may be used to evaluate lesions in the neck, chest, abdomen, and pelvis; and as a baseline evaluation for patients who may have brain metastases. The PET-CT is encouraged to be performed from baseline. However, when CT is the routine method to monitor patients according to hospital standard of care, PET-CT is not required. Evaluation of nodal lesion and extranodal lesion will be performed according to the revised criteria for response assessment in lymphoma [[Cheson 2014](#)] (see Section 9.4). Skin lesions are non-target lesions. Their response will be assessed according to mSWAT, and contribute to overall response determination.

Tumor response based on imaging studies will be confirmed with central review by independent radiologists at end of study prior to final efficacy analysis. The dates of PR, CR and PD will be assessed as applicable. Initial review will be performed by one independent radiologist. If the results differ from those reported by the investigators based on local radiology findings, a second independent radiologist will be asked to adjudicate by way of assigning the final disease response to the determination made by either the investigators or independent radiologist. The overall efficacy review will be done by independent oncologist for final efficacy analysis.

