9.4.6 Evaluation by Modified Severity-Weighted Assessment Tool (mSWAT) (Olsen et al. 2011)

A total of body surface area (%BSA) of each part is defined in Table 6 and Figure 4 (e.g., head 7, neck 2, and anterior trunk 13) in which total body surface area of human is defined as 100.

After %BSA of each type of lesion (patch, plaque, tumor mass, or ulcer) and normal skin is assessed by body parts, percentage of total body surface area (%TBSA) of each type of lesion will be calculated by adding %BSA of total body by type of lesion. In addition, mSWAT score is defined as summation (0 to 400) of product of %TBSA and each summation factor (see the following formula).

$$\text{mSWAT score} = (\% \text{TBSA of patch} \times 1) + (\% \text{TBSA of plaque} \times 2) + (\% \text{TBSA of tumor mass} \times 4) + (\% \text{TBSA of ulcer} \times 4)$$

Table 6: Modified Severity Weighted Assessment Tool (mSWAT)

Body Region	% BSA in Body Region	Assessment of Involvement in Patient's Skin		
		Patch*	Plaque**	Tumor***
Head	7			
Neck	2			
Anterior trunk	13			
Arms	8			
Forearms	6			
Hands	5			
Posterior trunk	13			
Buttocks	5			
Thighs	19			
Legs	14			
Feet	7			
Groin	1			
Subtotal of lesion % BSA				
Weighting factor				
Subtotal lesion BSA X weighting factor				

NOTE. mSWAT score equals summation of each column line.

[figure not shown]
Abbreviations: BSA, body surface area

*Any size lesion without induration or significant elevation above the surface- rounding uninvolved skin; poikiloderma may be present.

**Any size lesion that is elevated or indurated; crusting, ulceration, or poikiloderma may be present.

***Any solid or nodular lesion >1 cm in diameter with evidence of deep infiltration in the skin and/or vertical growth.

Figure 4: Percentage BSA of each Part of Human Body

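### The mSWAT loss-of-response rule compares an increase, counted from an unstated point, with a score level; either literal reading can only delay skin PD

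*Combined protocol and SAP*

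**What the plan says.** Section 9.4.9.3 (Appendix D) grades skin lesions by mSWAT. CR is "100% clearance of skin lesion" and PR is "50 to 99% clearance of skin disease from baseline without new lesion". PD can arise in three ways: a rise of 25% or more or a new mass ("increase in skin disease from baseline or New tumor mass"), or loss of response. Loss of response applies "in those with complete or partial response" and is defined as an "increase of skin score of greater than the sum of nadir plus 50% baseline score". The section gives no formula, no worked example and no reference point for the increase, and no other current section supplies one.

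On the role of skin response, Section 3.1.1 says: "Their response will be assessed according to mSWAT, and contribute to overall response determination". Section 5.9 has independent oncology reviewers judge lesions that imaging cannot follow. Section 3.5.4 has independent oncologists assign the dates of response and progression. Section 3.1.2 measures DOR from first response to PD, and PFS from first dose to objective progression or death. Under Sections 2.6.3 and 2.6.6, mSWAT scores and isolated skin progression do not decide whether treatment stops.

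**The concern.** Nadir plus half of baseline is a level that a score can cross. The sentence instead asks the increase to exceed that level. If the increase is counted from nadir, nadir enters twice. If it is counted from baseline, as the other percentage changes in the same list are, the bar is higher still. In both cases the clause can be overtaken by the 25% rule beside it, although its purpose is to catch responders who relapse before they are 25% worse than at baseline.

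At stake is the date of skin progression in patients with a skin response. Because isolated skin progression does not end treatment, a patient can stay on drug with stable or responding imaging while the skin relapses. In that patient the skin rule may influence the PD date used for DOR and PFS. A later date makes both look longer, in a single-arm study that Section 5.1 describes as pivotal. Two reviewers could also date the same patient differently.

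**Working it through.** The plan states no threshold figure to reproduce, so this is threshold algebra on the definitions.

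**Inputs (all Section 9.4.9.3)**
- B = baseline score, N = nadir, S = current score.
- Skin CR: N = 0. Skin PR is 50 to 99% clearance, so N runs from 0.01B to 0.50B.
- General rule: a rise of 25% or more from baseline, so S ≥ 1.25B. I take skin disease here to mean the mSWAT score.

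**Three readings of the clause**
- Score test: S > N + 0.5B.
- Literal, increase counted from nadir: S − N > N + 0.5B, so S > 2N + 0.5B.
- Literal, increase counted from baseline: S − B > N + 0.5B, so S > N + 1.5B.

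For each literal reading, the earliest PD by score is the lower of its threshold and 1.25B. The delay is that value minus (N + 0.5B). All entries are multiples of B.

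| N | Score test | From nadir: clause | Earliest PD | Delay | From baseline: clause | Earliest PD | Delay |
|---|---|---|---|---|---|---|---|
| 0 (CR) | 0.50 | 0.50 | 0.50 | 0 | 1.50 | 1.25 | 0.75 |
| 0.10 | 0.60 | 0.70 | 0.70 | 0.10 | 1.60 | 1.25 | 0.65 |
| 0.20 | 0.70 | 0.90 | 0.90 | 0.20 | 1.70 | 1.25 | 0.55 |
| 0.30 | 0.80 | 1.10 | 1.10 | 0.30 | 1.80 | 1.25 | 0.45 |
| 0.375 | 0.875 | 1.25 | 1.25 | 0.375 | 1.875 | 1.25 | 0.375 |
| 0.40 | 0.90 | 1.30 | 1.25 | 0.35 | 1.90 | 1.25 | 0.35 |
| 0.50 | 1.00 | 1.50 | 1.25 | 0.25 | 2.00 | 1.25 | 0.25 |

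**Crossover, counted from nadir.** 2N + 0.5B = 1.25B gives N = 0.375B. Below that point the delay equals N; above it the delay is 0.75B − N. The maximum is therefore 0.375B.

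**Counted from baseline.** The lowest threshold is 1.5B (at N = 0), already above 1.25B, so the 25% rule is met first in every responder, including skin CR.

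**Score test.** The threshold runs from 0.50B (CR) to 1.00B (PR at N = 0.50B). It is always below 1.25B, so the clause can act first for every patient it names. Of the three readings, only this one does so.

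**Examples with B = 40 (25% rule at 50)**
- N = 8: score test > 28; from nadir > 36; from baseline, 50 through the 25% rule.
- N = 12: > 32; > 44; 50.
- N = 20: > 40; from nadir the clause needs > 60, so PD comes at 50 through the 25% rule; from baseline, also 50.

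A responder with N = 0.30B who regrows to 1.0B has skin PD on the score test (1.0B > 0.80B). On neither literal reading does that patient (1.0B is below both 1.10B and 1.25B).

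**The case against.** The best defence is that the literal readings are self-defeating, so expert reviewers would probably apply the score test anyway. The protocol also cites a published mSWAT source, and a review charter may hold the formula. Neither is among the documents, so this cannot be confirmed. It lowers the practical risk but leaves the written definition wrong.

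Several stronger conclusions are tempting, and the documents do not support them:

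- **That the clause can never fire.** With B = 100 and N = 40, counted from nadir, it is met above 130, well within the 0 to 400 scale of Section 9.4.6. It is redundant because the 25% rule is met at 125. It is out of reach only at high baselines: B = 320 and N = 128 would need a score above 416.
- **That 37.5% of baseline is a property of the text.** It holds only if the increase is counted from nadir, which the section does not say.
- **That skin relapse is always dated late.** Counted from nadir, skin CR is unaffected. A new tumor mass is PD on any reading.
- **That the clause by itself sets the PD date.** Skin lesions are non-target, and skin response only contributes to overall response. No section says that isolated skin PD alone fixes overall PD. The CT column of Table 7 also counts clear progression of existing nonmeasured disease, and regrowth of resolved lesions, as PD. The Table 7 notes list cutaneous lesions among nonnodal disease, so reviewers have other routes.
- **That the primary result is biased.** The clause applies only after a response has been reached, so ORR is essentially untouched.

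It is also fair to say that no effect in weeks can be derived. Tumor response is assessed every 8 weeks, so a shift in threshold may move the PD visit by none, one or more visits.

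**Conclusion.** The point holds as a drafting error in an endpoint definition. The clause tests the wrong quantity and leaves its reference point open. Followed exactly, it never dates skin PD earlier than the score test. Counted from nadir, it raises the score needed in every skin PR, by up to 0.375B. Counted from baseline, the clause adds nothing to the 25% rule for any responder.

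The consequence is limited to possible lengthening of DOR and PFS, both secondary and summarised descriptively, in skin responders whose PD is not already determined by imaging, a new tumor mass or Table 7. The documents do not give the number of patients with skin disease, so the effect on the medians cannot be sized. The conclusion assumes that the 25% rule is applied to the mSWAT score, and that no formula outside these documents already settles the reading. This is a minor point, worth correcting because the correction is simple.

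**What to change.** Replace the loss-of-response wording in Section 9.4.9.3 with one inequality on the score: for a patient who has reached skin CR or PR, loss of response is a skin score greater than the nadir score plus 50% of the baseline score (S > N + 0.5B). Have the independent reviewers apply the same formula, and record it in their review instructions.

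The cost is one sentence. No new data are needed, because recorded mSWAT scores can be re-evaluated. Treatment decisions are not affected, since the protocol does not base discontinuation on mSWAT. The downside is that some skin PD dates, and hence DOR and PFS, may become slightly earlier.
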